### **Aim 1: Identify and enroll 20 pediatric patients with ASBI and PSH.**

**Methods:** Parent(s)/legal guardians, 18 years or older, will be approached for informed consent if their child has ASBI and is exhibiting clinical signs and symptoms of PSH. Once consented, the CFS scoring tool (Table 1a,) will be used to evaluate patients felt to be exhibiting symptoms of PSH to identify eligible ASBI patients. Patients with CFS score > 6 will be eligible for enrollment in the study.

Families of patients who do not meet the CFS score criteria > 6 will be told their child did not meet scoring criteria of study and will be considered consented but not enrolled in study.

Study Enrollment is defined as meeting CFS criteria of > 6 after consent. If CFS scores are already being collected for subject prior to subject consent as a standard of care, we can use already available CFS scores from medical record. The PENFS device will be placed over the external ear by study investigator or one of trained nurses (RNs) from the Pediatric Translational Research Unit (P-TRU) within 24 hours of meeting CFS > 6 score criteria..

There are 380-400 PICU admissions/year that are seen by ICU Neurology. Using a conservative estimate of 8-10% incidence of PSH, we expect to have 35-40 patients with PSH. At a conservative 60% enrollment rate, we expect to be able to successfully enroll 20 patients in this pilot study. Previous studies using the device has shown it to be well-tolerated with minimal side effects (25,26). In a large, randomized sham-controlled trial Kovacic et al showed a very low rate of discontinuation of the device due to side effects. We hypothesize that the dropout rate will be ≤ 10%. Tolerability of the device will be assessed by subjective assessments of device tolerance by the bedside nurse, the CFS score (increasing score after device placement would suggest worsening PSH symptoms) and skin integrity (bedside nurses will perform routine skin evaluation and care while the device is in place.). To evaluate safety, we will monitor for serious adverse effects such as cardiac dysrhythmia (EKG monitoring), and new-onset seizures.

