### **Aim 2a: Evaluate feasibility of scoring PSH symptoms using the PSH scoring tool**

**Methods:** The CFS (Table 1a) will be used to score the severity of PSH using the pediatric adaptation for the appropriate age range (Table 2 – diastolic blood pressure will not be used for scoring). CFS scoring will be performed by the bedside nurse who will be trained in using the scoring tool. PSH severity for the 12-hour period prior to placement of the device will be calculated retrospectively based on the features of CFS. After placement of the device, patients will be scored prospectively every 12 hours while the device is worn. The device will be discontinued after 120 hours of wear (usual duration of wear of a device). Scoring will be continued every 12 hours until 120 hours of device placement and then for another 72 hours (total of 192 hours for complete study duration). Every CFS score will be based on the severity of PSH symptoms in the preceding 12 hours.

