### **Aim 3b: Evaluate feasibility of measuring PENFS effectiveness in treating PSH by a decrease in medication use**

**Methods:** The maintenance medications and the number of doses and type of rescue medications administered will be collected for every 24 hours (0-24h, 25-48h, 49-72h, 73-96h, 97-120h, 121-144h, 145-168h, 169- 192h) for the enrolled patients. These will be compared to a historical cohort of PSH patients. The historical cohort will consist of PSH patients (2-17 years old) identified using the ICU Neurology administrative dataset from January 2018 – August 2021. This dataset will be used to identify ASBI patients who likely developed PSH. Eligible patients with PSH will be identified and relevant data collected by individual chart review. During this period all the PSH patients were followed by ICU Neurology thus ensuring a uniform approach to their treatment. We have also developed a practice guideline for treatment of PSH that will ensure uniform treatment of these patients during the study period. Similar to Aim 2a, we will examine the need for additional maintenance medications or change in frequency of rescue medications with discontinuation of the device. We hypothesize that, with discontinuation of the device, the patients may experience worse PSH symptoms as demonstrated by increasing CFS score and need for additional maintenance and/or rescue medications.

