## Protocol Summary/Submission Application

complete the study. If the patient does meet CFS scoring criteria for study enrollment, we will collect the CFS score for a 12-hour period before placement of the device followed by every 12 hours while the device is in place and for an additional 72 hours after removal of the device.

**Data collection & Management:** We will collect demographics, cause of ASBI, imaging findings, sedative, pain and other neurotropic medications, and maintenance and rescue medications for PSH including their number and doses for every 24-hour period from placement of the device. We will also collect all the HRV and pupillometry parameters for the 12-hour period before and after placement of the device. For the historical cohort, we will collect demographics, cause of ASBI, imaging findings, maintenance and rescue medications used in each 24 hour period for the first 120 hours and then additional 72 hours from the time of meeting CFS score > 6 criteria. . The REDCap database for this study will be developed and managed by Quantitative Health Sciences on MCW-secure servers

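### Historical controls enter at CFS > 6, but their qualifying score is not kept, has no stated derivation rule and is not adjusted for in the Aim 3b dose comparison

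*Combined protocol and SAP*

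**What the plan says.** **Source of controls.** Aim 3b Methods describes PSH patients "identified using the ICU Neurology administrative dataset from January 2018 – August 2021". It continues: "This dataset will be used to identify ASBI patients who likely developed PSH". Then: "Eligible patients with PSH will be identified and relevant data collected by individual chart review". Section 3, item B adds that the first pull of record numbers comes from billing data on broadly defined TBI.

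**Control data and time zero.** Section E, Data collection & Management: "For the historical cohort, we will collect demographics, cause of ASBI, imaging findings, maintenance and rescue medications used in each 24 hour period", for 120 hours and then an "additional 72 hours from the time of meeting CFS score > 6 criteria".

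**Device children.** The same section collects their CFS for the 12 hours before placement and 12-hourly to 192 hours. Aim 2a Methods says: "CFS scoring will be performed by the bedside nurse who will be trained in using the scoring tool". It also says: "PSH severity for the 12-hour period prior to placement of the device will be calculated retrospectively based on the features of CFS". For entry, Aim 1 Methods and Section 4, item B add that where scores already exist as standard of care, "we can use already available CFS scores from medical record".

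**Analysis and purpose.** Hypothesis 3b in the data analysis overview compares dose counts with historic data by t-test or Mann-Whitney. It then adds a classification tree on demographics, clinical history and device use. CFS is not named in either. The Aim 3b statement under item C says the comparison is there to support power and sample size for a later efficacy trial, and that this pilot is not powered for efficacy.

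**The concern.** Rescue and maintenance doses are given in response to symptoms, so severity at entry drives the Aim 3b outcome directly. Entry is by a threshold, and section E itself expects many consented children to fall below it. How the score is obtained therefore decides who enters and how ill they are.

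For controls, nothing states which items count, which reading within the 12-hour window is taken, or what is done when sweating or tone is not charted. The age table is also unsettled: Aim 1 points to Table 1a for eligibility, and Aim 2a to the paediatric adaptation in Table 2. If these choices differ between cohorts, severity differs at entry. Because the control score is not on the list of retained data, nobody could later see the difference or allow for it.

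What is at stake is the next trial. Required sample size goes with the inverse square of the assumed difference. A difference inflated by case mix would undersize that trial; a masked one would oversize it or end the programme.

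**Working it through.** The plan states no effect size, SD, alpha or cohort size for this comparison, so there is no figure to reproduce. The check is textual first, then illustrative.

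**1. The two cohorts side by side**

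| | Device children | Historical controls |
|---|---|---|
| Entry | CFS > 6 | CFS > 6 |
| Source of score | Bedside, or already in the record; pre-device window scored retrospectively | Chart review, no rule stated |
| CFS retained | Yes, before placement and 12-hourly | Not listed |
| Used in the Aim 3b test | No | No |

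**2. Threshold arithmetic.** With diastolic pressure left out, as Aim 2a specifies, the scale has 6 items scored 0-3, maximum 6 × 3 = 18. Sweating and posturing/tone carry 2 × 3 = 6 points. If both were uncharted and counted as zero, the maximum would be 4 × 3 = 12, and a child would need 7 of 12 on vital signs instead of 7 of 18.

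**3. Illustration with an inert device.** All inputs below are assumptions, apart from the 6-item structure, the entry threshold and the 20 device children.
- Latent severity s ~ N(0,1). Each item is 0.8s + 0.6e, with e ~ N(0,1), cut at -0.5, 0.5 and 1.5. There are 400,000 simulated children.
- Device children enter on a single complete 6-item score > 6. Controls enter by the rule in each row.
- Doses per 24 h are Poisson with mean 4·exp(b·s), times a gamma factor of mean 1 (shape 2, scale 0.5), with b = 0.2 or 0.4.
- 20 device children are compared with 20 or 100 controls by two-sided Mann-Whitney at 0.05, so 2.5% is nominal in each direction. With 3,000 runs the Monte Carlo error is √(0.025 × 0.975/3000) ≈ 0.3 percentage points.
- The choice of 100 controls is plausible: 380 × 0.08 = 30.4 to 400 × 0.10 = 40 PSH patients a year, over 44 months (× 44/12), gives about 111 to 147.

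| Control scoring rule | Share eligible | Mean s | Mean full CFS | Device v control doses, b = 0.2 / 0.4 | Significant for PENFS | Significant against |
|---|---|---|---|---|---|---|
| Same as device | 46.2% | 0.810 | 10.27 | 0% / 0% | 1.9-2.4% | 2.6-3.2% |
| Two items always absent, scored 0 | 23.4% | 1.208 | 12.31 | -7.5% / -14.2% | 4.6-10.4% | 0.3-1.1% |
| Each of the two absent in half of charts, scored 0 | 35.5% | 0.955 | 11.02 | -2.8% / -5.5% | 2.7-4.3% | 1.1-2.5% |
| Peak of 3 readings, items complete | 69.4% | 0.484 | 8.32 | +6.5% / +12.8% | 0.6-1.4% | 3.7-7.6% |
| Peak of 3, two items scored 0 | 44.7% | 0.839 | 9.95 | -0.5% / -1.0% | 2.2-2.7% | 1.8-2.5% |

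The dose difference is (device mean ÷ control mean) - 1. For b = 0.2 with two items always absent: 4.74/5.13 - 1, which is -7.5% before rounding. In the peak rows the full CFS is a fresh single reading, so part of the drop is regression to the mean; mean s is the cleaner comparison.

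Prorating the four vital-sign items (sum × 6/4 > 6) brings controls back to mean s 0.820 and mean full CFS 10.32, close to the device cohort.

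**4. Worst case in CFS points.** In the always-absent row the shift is 12.31 - 10.27 = 2.04 points. Nine further scenarios with item loadings of 0.3-0.7 gave 1.4 to 1.9 points. These figures require both items to be missing from every control chart and scored zero.

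**The case against.** *This is an unpowered pilot.* The plan says so, calls its 20 patients a convenience sample and concedes that randomisation would be better. This stands and limits the harm to planning. It does not remove the harm, because planning is the stated use of the comparison.

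*Other information covers case mix.* Cause and imaging are kept, and the tree uses clinical history. That is partial cover. Control CFS cannot enter the tree if it is not collected. The general missing-at-random and imputation text does not help either: for a variable absent in a whole cohort, imputation would have to borrow the device children's relationships. The uniform-treatment argument in Aim 3b concerns how children were managed, not how ill they were at entry.

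*A reader might infer that controls enter on rebuilt scores and device children on a nurse's fresh score.* The documents do not support so sharp a contrast. Record scores are allowed for device entry, the pre-device window is scored retrospectively, and some historical scores may already be charted.

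*A reader might infer that controls are picked by their PSH drug orders, and so on the outcome.* No passage says this. The first pull is by broad TBI criteria, followed by chart review and the CFS threshold. The lack of an explicit bar is not evidence of the practice.

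*Scoring uncharted items as zero is an assumption.* That is correct, and the result depends on it.

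**Conclusion.** The point holds as a design weakness of unknown sign. The control's qualifying CFS is needed to set time zero, yet it is not among the retained data. It has no common derivation rule, and the Aim 3b test does not adjust for it. That much follows from the text alone.

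A reader might go further and conclude that the comparison is tilted towards PENFS. The documents do not support that. Absent items scored zero make controls more severe, peak readings make them milder, the two together nearly cancel, and equivalent scoring gives no shift.

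Under the assumed inputs the apparent effect of an inert device lies between about 14% fewer and 13% more doses. One-sided false significance reaches at most about 10% for PENFS and 8% against, where 2.5% is nominal. The 1.4-1.9 point CFS shift (2.0 in the calculation above) is a worst-case illustration only. All these sizes rest on an assumed item model and an assumed link between severity and dosing; the documents give neither.

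**What to change.** In Aim 3b Methods, Data collection & Management, and Hypothesis 3b:

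1. Record for every historical child the qualifying CFS by item, with its source and time.
2. Derive the index CFS in both cohorts from the chart by one written rule: the same age table, the same fixed item set, the same choice of reading within the 12-hour window, and the same handling of uncharted items. Do not add sweating or tone only where charted, because that brings unequal item availability back. Re-score device children this way even if they entered on a bedside score.
3. Have the index CFS abstracted without sight of the drug record where possible.
4. Report the Aim 3b comparison adjusted for index CFS, with the unadjusted result alongside. Carry the adjusted estimate and its interval into the planning of the next trial.

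In the illustration, a common entry rule returned the expected difference to 0%. Adjustment alone was not simulated, and a single noisy score would leave some residual confounding, so item 2 matters as much as item 4.

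The cost is modest abstraction time, since the control score must be established anyway to start the clock, plus 20 re-scored device charts and a somewhat wider interval.

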## Protocol Summary/Submission Application

place that would normally be used to treat PSH. Additional maintenance medications could be instituted beyond the initial 12-hour period if PSH symptoms are not adequately controlled. Initiation of maintenance medications before placement of PENFS will not be a contraindication to enrollment, but once enrolled, no new maintenance medications would be allowed for the initial 12 hours after device placement.

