**Table 3: Data collection plan**

	-24 to -12 h	-12 to 0h	Device place ment 0 h		6h	12h	24h	24- 48h	48- 72h	72- 96h	96- 120h	120- 144h	144- 168h	168- 192h
Consent	x													
CFS score		x	x			x	X 12 hourly	x 12 hrly						
Pupillometry		x	x		x	x								
HRV using EKG		x	x		x	x								
Maintenance meds 		x				x	x	x	x	x	x	x	x	x
Rescue Meds 		x				x	x	x	x	x	x	x	x	X
Adverse Events						x	x	x	x	x	x	x	x	X

 No additional new Maintenance Medications are allowed for the first 12 hours after device placement. Patients may remain on Maintenance Medications they are already taking. Additional Maintenance Medication are allowed after the first 12 hours of device placement.

 Patients may continue Rescue Medications during the first 12 hours of device placement.

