## Protocol Summary/Submission Application

*Hypothesis 1:* The number approached and consented will be tracked. Reactions/ adverse events will be summarized and reasons for early termination, if any, evaluated.

*Hypothesis 2a, 2b:* The scoring tool will be adapted for the appropriate age range of the patient (Table 2). We aim for at least 80% scoring ( $\geq 8/10$  scheduled scoring per protocol while the device is worn). The association of the score and the number of doses of maintenance and rescue medications will be summarized with a spearman correlation and exact 95% Confidence intervals (CI).

*Hypothesis 3a:* HRV and Pupillometry measures will be tracked over time with any loss of data recorded with reasons. Wilcoxon Rank Sum test will be used to compare the mean  $\pm$ SD for the parameters for the 12-hour periods before and after device placement.

*Hypothesis 3b:* The number of doses of maintenance and rescue medications for control of PSH symptoms will be compared to historic data using a t-test or non-parametric Mann Whitney. Further a classification tree will be used to evaluate the effect of demographics, clinical history and use of PENFS.

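### The Aim 3b comparison with historical patients has no planned adjustment for prior medication use, because that use is listed for the device cohort only and time zero differs between the cohorts

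*Combined protocol and SAP*

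**What the plan says.** All references are to the combined protocol and SAP, mainly section E (Design and methods).

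- **Historical patients.** Under Data collection & Management: "For the historical cohort, we will collect demographics, cause of ASBI, imaging findings, maintenance and rescue medications used in each 24 hour period", and the window runs "for the first 120 hours and then additional 72 hours from the time of meeting CFS score > 6 criteria". Nothing before that time point is listed.
- **Device patients.** The same paragraph collects PSH drugs "including their number and doses for every 24-hour period from placement of the device". Table 3 adds a baseline: the "Maintenance meds" row and the rescue row are both marked in the -12 to 0 h column.
- **Entry on treatment.** Under Medication detail during study treatment: "Initiation of maintenance medications before placement of PENFS will not be a contraindication to enrollment".
- **Lag to placement.** Under Aim 1, the device goes on "within 24 hours of meeting CFS > 6 score criteria".
- **Analysis.** Under Hypothesis 3b, dose counts are "compared to historic data using a t-test or non-parametric Mann Whitney". A classification tree on demographics, clinical history and device use follows. Neither sentence names prior medication.
- **Purpose.** Section C says the comparison serves to plan a larger trial and that the pilot lacks power for efficacy.

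**The concern.** The comparison is not randomised, so it depends on the two cohorts being alike at time zero. Drug use just before time zero is an obvious candidate predictor of drug use just after. The plan lets it vary among device patients, records it for them, and does not list it for the historical patients. A baseline held in one cohort only cannot be used to compare the two.

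The clocks also differ. A device patient's first 24 h may begin up to a day after CFS exceeds 6, while a historical patient's begins at that moment. Section 2 says PSH symptoms are worst early and then ease, so a shift of up to a day can by itself change dose counts.

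What is at stake is the effect estimate handed to the next trial. If the pre-index window is not abstracted, no later analysis can adjust for it without reopening the charts.

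**Working it through.** **Stated figure.** The plan gives no alpha, SD, effect size or power for this comparison, so there is no figure to reproduce. What follows is illustrative.

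**Inputs from the documents.**
- Device patients: 20, a convenience sample (section 6, item D).
- Historical cohort: size not stated. The period January 2018 to August 2021 is 44 months. The Aim 1 figures of 380–400 admissions a year and 8–10% incidence give 380 × 0.08 = 30.4 to 400 × 0.10 = 40 PSH patients a year. Over 44/12 years that is about 111 to 147 at most.

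**Assumptions.**
- No true device effect; two-sided 5% test.
- Baseline imbalance d = 0.25, 0.5 or 0.8 SD.
- Baseline–outcome correlation r = 0.3, 0.5 or 0.7.
- Historical n = 20, 40, 111 or 147.

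**Spurious difference.** Unadjusted, it is r × d in SD units. With r = 0.5 and d = 0.5 it is 0.25 SD. A larger historical cohort does not reduce it. In dose units the pass-through is r × (SD after / SD before). If the SDs are equal and r is 0.5–0.7, an imbalance of 1 dose per 24 h adds 0.5–0.7 doses per 24 h.

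**Rejection rate of the unadjusted test.** Φ(rd/SE − 1.96) + Φ(−rd/SE − 1.96), with SE = √(1/20 + 1/n). For n = 40, SE = √0.075 = 0.274 and 0.25/0.274 = 0.913, so the rate is Φ(−1.047) + Φ(−2.873) = 0.148 + 0.002 = 15.0%. At r = 0.5:

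| Historical n | d = 0.25 | d = 0.5 | d = 0.8 |
|---|---|---|---|
| 20 | 6.8% | 12.4% | 24.4% |
| 40 | 7.4% | 15.0% | 30.9% |
| 111 | 8.1% | 17.7% | 37.7% |

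Over the whole grid the range is 5.6% (n = 20, d = 0.25, r = 0.3) to 65.2% (n = 147, d = 0.8, r = 0.7).

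**Check by simulation** (4,000 trials per scenario, normal data). At n = 40, d = 0.5, r = 0.5, the t-test rejects 14.7%, Mann-Whitney 14.1% and the baseline-adjusted linear model 5.0%. With d = 0 the unadjusted tests stay at 4.2–5.4%. The adjusted model stays at 4.5–5.8% in every scenario simulated, given the same baseline window in both cohorts, a linear relation and no other confounding.

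**Effect on the next trial.** With 80% power and two-sided 5%, n per arm = 2(1.96 + 0.84)²/δ², or about 15.7/δ². A true 0.5 SD effect needs 15.7/0.25 ≈ 63 per arm. If 0.25 SD of bias makes it look like 0.75 SD, the plan would call for 15.7/0.5625 ≈ 28.

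**Why the windows must match.** Device patients' -12 to 0 h window ends at placement. If placement comes 12–24 h after CFS exceeds 6, that window lies wholly after the threshold; with a shorter lag it lies partly after. A historical window ending at CFS > 6 lies wholly before. Suppose the timing alone gives device patients 1 extra baseline dose per 24 h. Adjusting at a slope of 0.5–0.7 would then move the estimate by 0.5–0.7 doses per 24 h in PENFS's favour.

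**The case against.** **The plan does have a covariate analysis.** The classification tree includes clinical history, and the analysis overview mentions mixed models for changes over time. It would therefore be wrong to say there is no covariate analysis at all. But clinical history is undefined, the listed historical data contain no prior drug use, and Hypothesis 3b does not name mixed models for this comparison. A tree cannot adjust for a variable that was not abstracted.

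**No imbalance is shown.** A reader might infer that the comparison will produce a false PENFS effect. The documents do not support that. Bias arises only if prior treatment differs, it could hide an effect as easily as create one, and with no imbalance the unadjusted tests hold their level. Aim 3b also argues for comparability: one service followed all historical patients, and a practice guideline applies during the study. Neither shows that the two periods were treated alike before time zero.

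**It is a feasibility pilot.** This stands, and it limits the harm to a biased planning estimate. It does not remove the harm, because planning is the stated purpose of the comparison.

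**The omission may be incomplete drafting.** Aim 3b allows relevant data to be taken from charts, and the device patients' own baseline drugs appear only in Table 3. The window could therefore be added, but nothing specifies it.

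**Conclusion.** The gap is real: no adjustment for baseline medication use is planned, the listed historical data would not permit one, and the two cohorts start their clocks at different events. If prior treatment intensity differs, roughly r × d SD of that difference enters the unadjusted estimate. That is 0.25 SD at d = 0.5 and r = 0.5, with rejection of 12–18% for historical cohorts of 20 to 111. These sizes rest on assumed values of d and r and on approximate normality. Whether an imbalance exists, and in which direction, is unknown. The point is worth acting on because the correction is cheap now and the estimate feeds the next sample size. Adjustment would remove only the part due to measured prior drug use, not other differences between the two periods.

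**What to change.** 1. **Aim 3b methods, Data collection & Management, and Table 3.** Use one common index time for the medication comparison in both cohorts, for example first meeting CFS > 6. Abstract maintenance and rescue drugs for the same 12 h before that index in both. For device patients this can reach back 24 + 12 = 36 h before placement, so Table 3's -12 to 0 h column alone will not cover it.
2. **Hypothesis 3b.** Make the main between-cohort estimate a regression adjusted for pre-index rescue-dose rate (12 h count × 2, as doses per 24 h) and number of maintenance drugs, with a 95% CI. Keep the unadjusted test and the tree as exploratory.

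Cost: one more window per chart in a review that is already planned patient by patient, and one or two degrees of freedom with about 20 device patients. If CFS > 6 is the index, up to 24 h of pre-device time counts in the device cohort's first period and may dilute an early effect. The report should say so.

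### Aim 3b starts the medication clock at device placement in enrolled children but at meeting CFS > 6 in historical children, so same-numbered 24-hour bins can cover different points of the illness

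*Combined protocol and SAP*

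**What the plan says.** Data collection & Management gives two different starting points. For enrolled children, PSH medication is recorded "including their number and doses for every 24-hour period from placement of the device", and Table 3 puts 0 h at device placement. For the historical cohort, medication is recorded in 24-hour periods "for the first 120 hours and then additional 72 hours from the time of meeting CFS score > 6 criteria".

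Aim 1 Methods, repeated in Section 4 item B, places the device "within 24 hours of meeting CFS > 6 score criteria". The qualifying score itself may come from two sources: "Study Enrollment is defined as meeting CFS criteria of > 6 after consent", but if scores are already charted as standard care, "we can use already available CFS scores from medical record". Aim 2a adds that "Every CFS score will be based on the severity of PSH symptoms in the preceding 12 hours".

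Aim 3b Methods lists the 24-hour intervals and says that they will be compared with the historical cohort. Hypothesis 3b, in the data analysis overview, compares numbers of doses by t-test or Mann-Whitney test, followed by a classification tree on demographics, clinical history and PENFS use. The Aim 3b statement among the specific aims gives the purpose: to support the power and sample size calculation for a later efficacy trial, while acknowledging that the pilot is not powered for efficacy.

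**The concern.** A comparison with historical controls needs time zero to mean the same thing in both groups. Here a historical child's first bin begins when the child meets CFS > 6. An enrolled child's begins when the device goes on, up to a day later. PSH severity and drug use change with time, so the two first bins, and every later pair, can describe different stages of the illness.

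This is a systematic difference, so recruiting more children would not remove it. Its practical consequence is for the next trial: the medication contrast that feeds the sample size calculation would mix any device effect with a shift of the clock.

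**Working it through.** **The plan's own figure.** 120 h of wear + 72 h of follow-up = 192 h, and 192 / 24 = 8 bins. This matches the eight intervals in Aim 3b Methods. There is no power or sample size figure for Aim 3b to reproduce.

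**Overlap of same-numbered bins.** Let L be the lag from the qualifying score to placement; the text permits 0 to 24 h. On a clock that starts at CFS > 6, a historical child's first bin is 0 to 24 h and an enrolled child's is L to L + 24 h. Shared time = (24 − L) / 24:
- L = 0 h: 100%
- L = 6 h: 18 / 24 = 75%
- L = 12 h: 12 / 24 = 50%
- L = 24 h: 0%

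**Does any planned analysis re-align them?** The t-test and Mann-Whitney test compare counts as recorded. The mixed models in the overview describe change over time, with no mention of a common origin. The tree's inputs are given only as categories, so whether the lag would be among them is unspecified. Table 3 marks medication for −12 to 0 h but not for −24 to −12 h. The planned data could therefore re-align lags up to 12 h, if dose times are kept, but not longer ones.

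**Illustration 1: rescue use falling from CFS > 6.** Section 2 item A says that symptoms are worst at first and then ease, but gives no rate. Let d be an assumed fall per day. With no device effect, the device cohort looks lower by 1 − (1 − d)^(L/24):

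| d per day (assumed) | L = 6 h | L = 12 h | L = 24 h |
|---|---|---|---|
| 2% | 0.5% | 1.0% | 2% |
| 10% | 2.6% | 5.1% | 10% |
| 30% | 8.5% | 16.3% | 30% |

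For example, d = 10% and L = 12 h give 1 − 0.90^0.5 = 5.1%.

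**Illustration 2: an early rise.** Assume that the rate of rescue use doubles linearly (0.5 to 1.0) over the first 24 h after CFS > 6 and then falls 15% per day, with L = 12 h. The device-to-historical ratio with no device effect is 1.22 in 0–24 h, 0.92 in 24–48 h and 0.98 over 0–120 h. The first bin now goes against the device, and the 120 h total hardly moves.

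**Illustration 3: the 12-hour bar.** New maintenance drugs are barred for 12 h after placement in the device cohort only (Medication detail during study treatment; Table 3, footnote 1). This may raise early rescue use. At d = 10% and L = 12 h, the rise in 0–12 h rescue use that cancels the shift is [1/(1 − 0.0513) − 1] / share of rescue use falling in 0–12 h:
- 0–24 h bin: share = 0.0513 / 0.10 = 0.513, so 0.0541 / 0.513 = 11%.
- 0–120 h: share = 0.0513 / (1 − 0.90^5) = 0.125, so 0.0541 / 0.125 = 43%.

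A modest rise would cancel the shift in the first bin; a larger one is needed over the whole wear period.

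**The case against.** The strongest reply is that this is a small feasibility pilot, open about its lack of power, and that the shift may be lost in noise. That is fair on size. With 20 enrolled children, an assumed 20 to 60 historical children and an assumed coefficient of variation of 0.5 to 0.8, the 95% half-width for the difference in means is 1.96 × CV × √(1/20 + 1/m), where m is the number of historical children. That is about 25% of the mean (CV 0.5, m = 60) to 50% (CV 0.8, m = 20), well above 5%. But noise does not cancel bias, and the estimate has a stated planning use. The within-patient comparison at device removal does not depend on the historical clock and is untouched.

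Three stronger readings are tempting, and the documents do not support them.

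- **That the mismatch favours PENFS.** The natural history statement, and the permission to start maintenance drugs before placement, point that way. But that statement has no timescale and does not begin at CFS > 6. An early rise or the 12-hour bar can reverse the sign. Children who still score above 6 after consent may also have more persistent PSH, which would raise device-cohort counts.
- **That the lag can exceed 24 h.** This needs the historical clock to start at the first score above 6. The text does not say first, and the 24 h limit runs from meeting the criterion.
- **That the cohorts are scored on different tables.** Aim 1 says "the CFS scoring tool (Table 1a,) will be used to evaluate patients", but Aim 2a scores "using the pediatric adaptation for the appropriate age range", and the specific aims and Hypothesis 2a also say that the tool is age-adapted. What remains is only that the historical cohort's scoring is not spelled out.

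**Conclusion.** The point stands as a misaligned time origin. Followed as written, the plan compares bins that can be offset by up to one full bin, and no stated analysis corrects this. A child fitted at once has no shift.

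The overlap figures follow from the text alone. The percentage shifts do not: decline rates, actual lags and the shape of the early course are all assumptions. Under steady decline the shift runs from 0.5% (2% per day, 6 h) to 30% (30% per day, 24 h), with about 5% at 10% per day and 12 h. A reader might go on to infer that the next trial will be undersized by a known amount. The documents support only that its planning input may be distorted, in an unknown direction and by an unknown amount.

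Severity is modest. Aims 1 and 2a do not use this comparison. It is still worth fixing before chart extraction, because qualifying times and dose times are easier to collect then than to recover later.

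**What to change.** 1. **One origin.** Define the qualifying CFS > 6 time by the same rule in both cohorts: same event, same score source, same age-adapted scoring and same point of the 12-hour scoring window. Record that time and the lag to placement for every enrolled child.
2. **Main comparison.** Count medication in both cohorts from the qualifying time. For enrolled children, extend collection from −12 h back to the qualifying time, at most −24 h, with dose times.
3. **Sensitivity analysis.** Count enrolled children from placement. Count historical children from the qualifying time plus the enrolled children's median lag, keeping only those still in the PICU at that point.
4. **Reporting.** Give the lag distribution, show the first 12 h after placement separately, and name the 12-hour bar as a remaining difference between cohorts. The clinical rule itself is not changed.

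Cost: Aim 3b already requires individual chart review, so the extra work is dose times and a slightly longer historical record, at most 192 + 24 = 216 h. Counting from CFS > 6 puts some untreated time in the enrolled children's first bin (half of it at a 12 h lag), which dilutes any early device effect; the sensitivity analysis addresses this. Historical children who left the PICU early drop out of that analysis. If CFS was not charted historically, it must be scored retrospectively, and sweating and posturing may be poorly recorded.
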